## 1. Background

### 1.1 Clinical assessment immediately after birth

Evaluation of a newborn infant immediately after birth could be a challenge. To standardize the clinical assessment Virginia APGAR introduced 1953 the so-called APGAR-Score, which is still used routinely worldwide, to evaluate the neonates in the delivery room. (1).

### 1.2 Monitoring immediately after birth

The latest resuscitation guidelines recommend in addition to the clinical assessment to monitor arterial oxygen saturation (SpO2) and heart rate (HR) immediately after birth in neonates in need of support (2).

However, since 1953 beside SpO2 and HR monitoring, further methods and parameters, which could be monitored have been described during the immediate transition after birth that might help to assess the neonate in this crucial period. These methods include cardio-circulatory monitoring of blood pressure or cardiac output (3–5), respiratory function monitoring (6), transcutaneous monitoring of pCO2 (7) and cerebral monitoring with (a)EEG or near infrared spectroscopy (NIRS) (10, 11).

### 1.3 Cardio-circulatory monitoring during immediate transition

Blood pressure on the one hand is a routine monitoring in the NICU measured invasively or with the oscillometric method non-invasively. During immediate neonatal transition in the delivery room, the invasive measurement is not feasible, whereby the oscillometric method has already been proven to be feasible. (13). Meanwhile, reference ranges for non-invasively measured arterial blood pressure have been published for preterm and term neonates (14).

Cardiac output on the other hand can be measured with noninvasive, minimal invasive and invasive methods (18). The gold standard method would be the so-called thermodilution technic, which is gained through a pulmonary vain catheter that is, however, quite invasive (19, 20). Cardiac output measurements are therefore performed routinely with the echocardiography especially in severely ill neonates in the NICU. The advantage of the echocardiography is that it is a non-invasive method and the disadvantages are that the quality of the echocardiography depends on the experience of the examiner and evaluation is non-continuous. Furthermore, the measurement itself has its limitation concerning feasibility when performed during resuscitation (4, 21, 22).

A further method to measure cardiac output is the electrical velocimetry. This method is based on the different electrical conductivity of certain biological tissues. Due to impedance changes during a heartbeat, the stroke volume can be assessed, and the cardiac output calculated (8). Electrical velocimetry monitoring is a feasible new method to measure cardiac output during the immediate transition after birth (9). Noori et al. showed that electrical velocity monitoring has regarding the cardiac output comparable results to echocardiography (12).

#### 1.4 Near-infrared spectroscopy (NIRS)

NIRS was first described and published by Jöbsis (23) in 1977. The basis of this technique are the physical properties of the organic tissue to light in the near infrared region. The light used has therefore a wavelength in the near infrared region (700-1000 nm) (11). This light is absorbed, scattered or reflected differently by different chromophores such as myoglobin, cytochrome oxidase, oxygenated or deoxygenated hemoglobin in the biological tissue. Due to this, it is possible to monitor continuously the tissue oxygenation that depends on oxygen supply as well as the consumption of different tissues such as brain, kidney, or muscles (11, 24, 25).

NIRS therefore is a continuous noninvasive monitoring of tissue oxygenation that reflects the tissue oxygen saturation in veins, capillaries, and arteries of the measured compartment (10, 25, 26).

With the knowledge of the SpO2 and the tissue oxygen saturation the fractional tissue oxygen extraction (FTOE) can be calculated (FTOE=(SpO2-tissue oxygenation/SpO2)). FTOE reflects the oxygen extraction of a tissue from the vessels, which helps to assess the activity of certain biological tissues (25, 27).

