## 3. Hypotheses:

### 3.1 Primary Hypothesis I

Non-invasive measured blood pressure correlates with cerebral oxygen saturation and cerebral fractional oxygen extraction, whereby higher blood pressure is associated with higher cerebral

oxygen saturation and lower cerebral fractional oxygen extraction in term and preterm neonates within the first 15 minutes after birth.

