## 9 Outcome measures

### 9.1 Primary

- Blood pressure minute 5, 10 and 15
- NIRS data measured with t-NIRS minute 5, 10 and 15
- FTOE minute 5, 10 and 15

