## 14 Data analysis

Initially, all data will undergo a descriptive analysis to uncover any data anomalies and missing values that may impact the validity of the data analysis.

Demographic, NIRS and routine monitoring data will be presented as n (%), mean and standard deviation (SD), or median and interquartile range (IQR), as appropriate.

Comparisons of categorical characteristics between preterm and term infants will be performed using chi-square test and for continuous variables using t-test or Mann-Whitney U-test, as appropriate.

Correlation analyses will be performed to investigate, if there is a connection between crSO2, cFTOE and MAP in preterm and term infants at different time points, individually. Correlations will be performed using Spearman's rank correlation coefficient or Pearson's correlation when appropriate. A p-value < 0.05 will be considered statistical significant. The statistical analyses will be performed using IBM SPSS Statistics 22.0.0 (IBM Corporation; Armonk, USA).

Comparison of correlation analyses at different time points and in term and preterm neonates will be descriptive. Statistical analysis is planned to be performed in cooperation with the Institute for Medical Informatics, Statistics and Documentation, Medical University of Graz, Austria.

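### Does the misplaced bracket in the Section 1.4 formula for FTOE put a primary outcome at risk?

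*Combined protocol and SAP*

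**What the plan says.** Section 1.4 explains that once SpO2 and tissue saturation are known, "the fractional tissue oxygen extraction (FTOE) can be calculated", and prints the expression "FTOE=(SpO 2 -tissue oxygenation/SpO 2" followed by the closing brackets. The next sentence gives the meaning: "FTOE reflects the oxygen extraction of a tissue from the vessels".

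The quantity then carries real weight:

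- Section 3.1 (Primary Hypothesis I) expects higher blood pressure to go with higher cerebral "oxygen saturation and lower cerebral fractional oxygen extraction in term and preterm neonates within the first 15 minutes after birth".
- Section 9.1 lists "FTOE minute 5, 10 and 15" among the primary outcomes.
- Section 14 plans correlations to see "if there is a connection between crSO 2 , cFTOE and MAP in preterm and term infants at different time points".

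None of these sections repeats the formula, states a derivation rule or gives units. Section 14 does open with a descriptive pass over all data "to uncover any data anomalies and missing values that may impact the validity of the data analysis".

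**The concern.** FTOE is not read from a monitor. It has to be derived from two signals, pulse oximetry and NIRS, so the derivation is part of the definition of the outcome. The only derivation in the document is printed with a bracket in the wrong place: by the usual order of operations, only tissue oxygenation is divided by SpO2.

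If somebody coded that line as it stands, the consequences would not be trivial. In percent units the result is SpO2 less a number between 0 and 1 (whenever tissue saturation is below SpO2), so it ranks infants almost exactly by SpO2. The planned correlation of blood pressure with oxygen extraction would in effect become a correlation of blood pressure with arterial saturation, which is a different question from Hypothesis I. In fraction units the distortion is smaller but grows as SpO2 falls, and low saturations are to be expected in the first minutes after birth. With no formula in Section 9.1 or Section 14 to override the background text, it is reasonable to ask whether the primary analysis is properly specified.

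**Working it through.** **Inputs.** The expression and the name of the quantity come from Section 1.4. The plan states no numerical FTOE value, so there is no figure of its own to reproduce. It also gives no distribution of SpO2 or tissue oxygenation, so every saturation below is an assumption. Write S for SpO2 and T for tissue oxygenation.

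**Step 1: one worked example, S = 85%, T = 65%.**

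- As printed, percent: 85 - 65/85 = 85 - 0.765 = 84.24.
- As printed, fractions: 0.85 - 0.65/0.85 = 0.85 - 0.7647 = 0.0853.
- As intended, either unit: (85 - 65)/85 = 20/85 = 0.2353.

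**Step 2: other assumed pairs.**

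| S / T (%) | Printed, percent | Printed, fractions | Intended |
|---|---|---|---|
| 60 / 45 | 59.25 | -0.150 | 0.250 |
| 80 / 60 | 79.25 | 0.050 | 0.250 |
| 90 / 70 | 89.22 | 0.122 | 0.222 |
| 95 / 60 | 94.37 | 0.318 | 0.368 |

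Only the intended form is free of units. In percent the printed form is close to S itself. In fractions it can be negative even when T is below S.

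**Step 3: the size of the fraction-unit error.** S - T/S = (1 - T/S) - (1 - S), so the printed value equals the intended FTOE minus (1 - S). In the example, 0.2353 - 0.15 = 0.0853. It is negative whenever T > S squared: above 72.3% when S is 85%, and above 56.3% when S is 75%.

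**Step 4: what literal coding would do to the ranks.** The assumed grid was SpO2 mean 75, 82 or 90 with SD 4, 8 or 12; tissue mean 55, 65 or 75 with SD 5, 8 or 12; and correlation 0, 0.4 or 0.8. That is 3 x 3 x 3 x 3 x 3 = 243 scenarios, each with 40,000 bivariate normal draws restricted to SpO2 30-100 and tissue 20-99.

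- Percent units, all 243 scenarios: Spearman correlation of the printed form with SpO2 is at least 0.999.
- In the 135 scenarios where fewer than 5% of intended FTOE values are negative, the printed percent form has a Spearman correlation with intended FTOE of -0.67 to 0.85.
- In the same scenarios the printed fraction form has a Spearman correlation with intended FTOE of 0.47 to 0.97 (median about 0.87).

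**Step 5: would it be noticed?** In percent units a supposed fraction would have values around 60 to 100, which no descriptive table could pass off as plausible. In fraction units, more than 5% of infants would have a negative extraction in 106 of the 135 scenarios (79%). In the remaining 29 the warning sign is weaker.

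**Step 6: does anything in the plan depend on the printed form?** The r = -0.19 in Section 5 is taken from a previous study. The confidence limits there are stated for assumed correlations and a number of infants. Neither uses the Section 1.4 expression, so correcting the bracket leaves every stated figure as it is.

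**The case for a change.** The strongest argument for acting is that a derived primary outcome ought to have a correct, explicit derivation rule in the outcome or analysis section, and this one has none. The only written formula is wrong as printed, the analysis is to be done in cooperation with a separate statistics institute, and the repair costs one bracket and one line. Nor is the anomaly check a complete safeguard: in the 29 scenarios with few negative values, the fraction-unit form still agrees with the intended FTOE at a Spearman correlation of only 0.47 to 0.96, so the check could miss that error.

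The arithmetic in this argument stands, and so does the remark that restating the formula in Section 9.1 would be good practice. What does not stand is the step from a misprint to a risk for the analysis. The fraction-unit case that might escape notice needs two unlikely acts together: both signals converted to fractions, and a background expression coded literally against its own name. The protocol treats cFTOE as an established measure. Section 1.6 discusses earlier findings on it, and Section 5 starts from a published correlation with it. An analyst who knows the quantity is a fraction has only one formula to choose. The brackets balance, so the slip cannot simply be put down to conversion of the PDF, though that possibility cannot be excluded either.

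**Conclusion.** The concern does not call for a change to the plan. The bracket in Section 1.4 is misplaced, and read literally the formula is wrong: 84.24 or 0.085 in place of 0.235 in the worked example. It is a clerical slip in background text. The wording beside it fixes the intended quantity as (SpO2 - tissue oxygenation)/SpO2, Sections 9.1 and 14 do not direct anyone to the printed expression, and no figure in the plan rests on it.

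The expected effect on the results is nil. This rests on the analyst deriving FTOE as the fraction its name describes, which is the ordinary reading. The simulated distortions describe only what literal coding would do, under saturation distributions that the documents do not give. The bracket may be corrected whenever the document is next edited, but the outcomes, the analysis and the sample size stay as they are.

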#### 1.5 Arterial blood pressure, cardiac output and cerebral oxygenation

The tissue oxygen saturation is not only depending on the SpO2 but also on the hemoglobin content of the blood, the perfusion and tissue oxygen consumption. Concerning the perfusion and considering the brain it would be the so-called cerebral blood flow (CBF), which depends on cerebral perfusion pressure (CPP). CPP is defined as the difference between intracranial pressure (ICP) and mean arterial blood pressure (MABP) (28–30). During immediate transition ICP measurement is not feasible due to the invasive technics through a catheter and ICP can be assumed to be constant during the transition period especially in preterm neonates where the sutures are not closed yet. In contrast to that, the MABP can easily be measured

even during the immediate transition non-invasively with an oscillometric method as discussed previously (13).

MABP itself depends mainly on CO and vascular resistance. In the peripheral tissue, i.e. muscle, an increase of the MABP correlates well with an increase of oxygenated hemoglobin. The correlation between the MABP and the cranial perfusion and oxygenation should be weaker, due to cerebrovascular response mechanism, known as cerebral autoregulation that should keep cerebral perfusion constant independently of MABP (31).

In sick neonates and in preterm neonates, however this autoregulation is not working as well as in healthy term infants (15, 17).

### 1.6 Physiological changes of the cardio—circulatory system during transition

The main difference of fetal cardio-circulation to the cardio-circulation after birth is that before birth the lungs are by-passed, and the oxygenated blood is provided by the placenta. The three bypasses are the ductus venosus (DV), a connection between the umbilical vein and the vena cava inferior, the ductus arteriosus (DA), a vessel between pulmonary artery and the aorta to avoid pulmonary circulation, and the foramen ovale (FO), a connection between the cardiac atria which also serves the purpose to bypass the pulmonary circulation.

Due to these described peculiarities the fetal circulation is a parallel circulation instead of a serial one (32, 33).

During transition, the pulmonary resistance drops, due to the lung aeration. This resistance-drop triggers an increase of the pulmonary blood-flow. Considering this new detour, depending on when the umbilical cord was clamped, the preload is reduced during the first minutes after birth. Furthermore, due to the cord clamping the low-resistance placenta circulation is yield, which leads to an increased afterload and the arterial pressure increases. As a result of reduced preload and initial-increased afterload, the cardiac output is reduced with clamping the cord.

Considering these changes, the cerebral blood-flow as well as the systemic blood flow and systemic blood pressure are initially increased whereby a drop occurs immediately after the initial increase due to the reduced cardiac output (34). Afterwards, the cardiac output continues to stay low until the pulmonary blood-flow increases with ventilation of the lungs (35). During this cardio-circulatory and pulmonary changes immediately after birth the cerebral autoregulatory mechanisms should maintain the cerebral blood-flow constant. These autoregulatory mechanisms are not yet fully comprehensible especially in preterm neonates (36, 37).

In term neonates Baik et al have demonstrated that cFTOE as well as crSO2 are independent of MABP (38, 39). However, Baik's study (38) only investigated MABP in connection with crSO2 as well as cFTOE 15 minutes after birth. However, the question remains, if in term neonates MABP has some influence on cerebral oxygenation before minute 15 after birth when the lung is aerated, and most cardio-circulatory changes take place.

Furthermore, Baik's study (38) showed a significant negative correlation between MABP and cFTOE in preterm neonates which seems to suggest that in preterm infants the autoregulatory mechanism are less mature than in term neonates and that preterm neonates may benefit from blood pressure monitoring during immediate neonatal transition. These findings are in accordance with the animal model of Helou and Rhees observation in neonates (15–17). However again the question remains, if in preterm neonates MABP has more influence on cerebral oxygenation before minute 15 after birth when the lung is aerating and most cardio-circulatory changes take place.

## 2 Aims

### 2.1 Primary aim

The primary aim of the present study is therefore to investigate if there is an influence of blood pressure on cerebral oxygen saturation and cerebral oxygen extraction within the first minutes (within 15 minutes) after birth in term and preterm neonates, when most cardio-circulatory changes and aeration of the lung take place.

### 2.2 Secondary aim

Secondary aims are to investigate a possible influence of cardiac output on cerebral oxygen saturation and cerebral oxygen extraction within the first minutes after birth in term and preterm neonates and any possible differences between term and preterm neonates.

## 3. Hypotheses:

### 3.1 Primary Hypothesis I

Non-invasive measured blood pressure correlates with cerebral oxygen saturation and cerebral fractional oxygen extraction, whereby higher blood pressure is associated with higher cerebral

oxygen saturation and lower cerebral fractional oxygen extraction in term and preterm neonates within the first 15 minutes after birth.

### 3.2 Secondary Hypotheses II

Cardiac output correlates with cerebral oxygen saturation and cerebral fractional oxygen extraction, whereby higher cardiac output is associated with higher cerebral oxygen saturation and lower cerebral fractional oxygen extraction, whereby correlations are more pronounced in preterm neonates within the first 15 minutes after birth.

## 4 Patients and Methods

### 4.1 Patients

Term and preterm neonates observed routinely at the resuscitation desk at the Division of Neonatology, Department of Pediatrics, Medical University of Graz after caesarean section and/or who require respiratory support will be eligible for the study. CPAP and PPV with mask, if necessary, will be performed with Neopuff Infant Resuscitator (Fisher&Paykel Healthcare, New Zealand).

The total number of birth/year at the Department of Obstetrics and Gynecology, Medical University of Graz is approximately 3000 - of these are around 8-10% preterm neonates.

The antepartum medical history and birth history will be collected. Gestational age, birth weight, gender, Apgar score, ph of umbilical artery and postnatal blood gases (if routinely analyzed) will be documented in each neonate.

#### 4.1.1 Inclusion criteria

- Term and preterm neonates observed routinely at the resuscitation desk
- Decision to conduct full life support
- Written informed consent

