#### 4.1.2 Exclusion criteria

- No decision to conduct full life support
- No written informed consent
- Congenital malformation

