## 2. Term neonates ( $\geq 37+0$ weeks of gestation)

## 5 Sample size

In preterm infants, it was found that the correlation between MABP, and cFTOE is  $r = -0.19$  at 15 minutes after birth. Even lower correlations were found for crS02 and MABP and for term infants (38). Due to the bevor in 1.6. described changes during the immediate transition period, which lead to a decrease in cardiac preload and an increase in cardiac afterload the cardiac output is reduced. Considering these changes in the cerebral blood flow as well as the systemic blood flow and systemic blood pressure we expect to find higher correlations in the fifth and tenth minute after birth. According to our experience, it is feasible to include 50 infants in this study. If 50 infants are included and a drop-out rate of 10% is considered, 45 infants can be analyzed. Using these 45 infants the lower limit of Spearman's rank correlation coefficient's 95% CI will be 0.14 for a correlation coefficient of  $r = 0.40$ . This lower limit increases to 0.20, 0.26, 0.32 for  $r = .45$ ,  $r = .50$  and  $r = .55$  respectively.

Therefore we aim for a sample size of 50 neonates in each group – preterm neonates and term neonates, resulting in a total sample size of 100 neonates

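### The plan does not say how siblings from one pregnancy are handled; if co-siblings are analysed as independent infants, p-values may be somewhat too small

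*Combined protocol and SAP*

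**What the plan says.** All references are to the combined protocol and SAP.

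- **Eligibility.** Section 4.1.1 includes "Term and preterm neonates observed routinely at the resuscitation desk". Section 4.1 describes the source population as infants "after caesarean section and/or who require respiratory support will be eligible for the study". Section 4.1.2 has three exclusions: no decision for full life support, no consent, and "Congenital malformation". Plurality appears in none of these places, so twins and higher multiples are eligible by silence.
- **Unit of the sample size.** Section 5 states "Therefore we aim for a sample size of 50 neonates in each group" and "If 50 infants are included and a drop-out rate of 10% is considered, 45 infants can be analyzed". The unit is the infant.
- **Precision.** Section 5 continues: "Using these 45 infants the lower limit of Spearman's rank correlation coefficient's 95% CI will be 0.14", for a coefficient of 0.40.
- **Analysis.** Section 14 states "Correlation analyses will be performed to investigate, if there is a connection between crSO 2 , cFTOE and MAP in preterm and term infants", separately by time point, using Spearman's or Pearson's coefficient with p < 0.05 as the threshold. It gives no one-infant-per-pregnancy rule, no clustering adjustment and no sensitivity analysis.
- **Data.** Section 4.1 states "The antepartum medical history and birth history will be collected". The items it then names for each neonate include neither plurality nor a sibling identifier, and section 13 says the CRF data are anonymized.

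**The concern.** Siblings from one pregnancy share gestational age and maternal treatment, and usually mode of delivery. These are plausible common influences on blood pressure and cerebral oxygenation in the first minutes of life. Each planned correlation is run within one group at one time point, so repeated measures on an infant are not pooled. Sibship is therefore the evident remaining source of dependence within a correlation.

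If co-siblings are analysed as unrelated infants, the standard error of the coefficient is understated. The p-values of section 14 would then be too small, and the lower confidence limits that justify the sample size in section 5 would be too favourable. Without a pregnancy identifier in the data set, the analyst might also be unable to check whether this has happened.

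**Working it through.** **Inputs from the documents.** 50 infants per group, 10% drop-out, 45 analysed (section 5); p < 0.05 (section 14; taken as two-sided, since sidedness is not stated).

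**Inputs assumed.** Two quantities are not in the documents:

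- *f*, the share of analysed infants whose twin is also analysed: 0.2 to 0.5, with 0.1 as a low case;
- the within-pair correlation (ICC) of blood pressure and of the cerebral measure: 0.3 to 0.7, taken as equal in both.

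**Step 1: the plan's own figures.** 50 × 0.9 = 45, as stated. The lower limit by Fisher's transformation is tanh(atanh(r) − 1.96/√(n − 3)).

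| r | Stated | n = 45 | n = 50 |
|---|---|---|---|
| 0.40 | 0.14 | 0.121 | 0.137 |
| 0.45 | 0.20 | 0.180 | 0.196 |
| 0.50 | 0.26 | 0.242 | 0.257 |
| 0.55 | 0.32 | 0.306 | 0.321 |

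The stated limits match n = 50, not the 45 to which section 5 attributes them. That is a separate matter, but it means the correct baseline here is 0.121 rather than 0.14.

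**Step 2: effect of pairs, by approximation.** Near zero correlation, the variance of r is multiplied by about

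DE = 1 + f × ICC(blood pressure) × ICC(cerebral).

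The effective n is 45/DE, the type I error is 2 × [1 − Φ(1.96/√DE)], and the lower limit at r = 0.40 is tanh(atanh(0.40) − 1.96 × √(DE/42)).

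| f | Both ICCs | DE | Effective n | Type I error | Lower limit at r = 0.40 |
|---|---|---|---|---|---|
| 0 | – | 1 | 45 | 5.0% | 0.121 |
| 0.1 | 0.3 | 1 + 0.1 × 0.09 = 1.009 | 44.6 | 5.1% | 0.119 |
| 0.2 | 0.3 | 1 + 0.2 × 0.09 = 1.018 | 44.2 | 5.2% | 0.118 |
| 0.3 | 0.5 | 1 + 0.3 × 0.25 = 1.075 | 41.9 | 5.9% | 0.110 |
| 0.5 | 0.7 | 1 + 0.5 × 0.49 = 1.245 | 36.1 | 7.9% | 0.086 |

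The design effect is derived near zero correlation, so the last column is a guide only.

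**Step 3: check by simulation.** Spearman's test was simulated under the null with n = 45 and shared pair effects in both variables.

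| Twin pairs (share of 45) | Both ICCs | Type I error |
|---|---|---|
| 0 | – | 5.0% |
| 5 (22%) | 0.3 | 5.1% |
| 7 (31%) | 0.5 | 5.9% |
| 11 (49%) | 0.7 | 7.6% |

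Repeat runs with other random seeds agreed to within about 0.2 percentage points. With 9 pairs, an ICC of 0.8 in one variable and 0 in the other, the error was 4.9%, so there was no inflation. Both variables must be alike within pairs, because the inflation depends on the product of the two ICCs.

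**The case against.** The strongest case against acting has five parts.

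1. **The harm is conditional.** A reader might infer that the p-values and intervals are too optimistic, that the effective sample is below 45 and that the 5% level is exceeded. The documents do not support that as fact. It requires both siblings to be analysed at the same time point and both variables to be alike within pairs, and neither quantity is given. This objection stands.
2. **It is not confined to preterm infants.** A reader might also infer that the problem sits in the one group where the plan expects an association. Section 3.1 states the primary hypothesis for term and preterm infants alike. Only the secondary cardiac-output hypothesis in section 3.2 expects stronger correlations in preterm infants. Term twins are eligible too. That preterm infants are more affected is plausible but undocumented. This stands.
3. **Co-enrolment may be rare.** Sections 7.3, 7.5 and 13 describe the NIRS device, the cardiac-output monitor and the recording system in the singular. With one set, siblings born minutes apart could seldom both have data at minutes 5, 10 and 15. The number of devices is not stated, so this is a reason to include low shares of pairs (5.1% error at f = 0.1 and ICC 0.3), not a reason to dismiss the point.
4. **The effect is small.** At the middle setting the error is 5.9%, and the lower limit moves by 0.121 − 0.110 = 0.011. That is less than the gap of 0.14 − 0.121 = 0.019 between the stated limit and the one that n = 45 gives. The study is an observational pilot (section 6) with at least 2 measures × 3 times × 2 groups = 12 primary correlations, each tested at an unadjusted 0.05. This stands and sets the priority.
5. **A cluster bootstrap gains little at the middle setting.** Simulated error was 5.4% with a bootstrap resampling mothers and 5.8% without, which is within simulation error. At the extreme it fell from 7.7% to 5.7%. Section 14 also names SPSS 22, and the ease of coding this there has not been shown. So the bootstrap should be one option, not a required main method.

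Section 14 plans p-values and names no confidence interval. The remark about intervals therefore concerns the projection in section 5.

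**Conclusion.** The gap is real: multiples are eligible, infants are the unit, and the planned tests have no provision for siblings. The consequence is conditional and modest. Over the assumed range the simulated type I error at n = 45 is about 5.1% to 7.6%, about 5.9% in the middle, and close to 5% if few siblings are co-enrolled. The upper end needs about half the analysed infants in pairs and within-pair correlations of 0.7 in both variables. These figures rest entirely on assumed pair shares and within-pair correlations. This is a cheap improvement of low priority, and it gives no reason to doubt the design.

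**What to change.** - **CRF:** add a pregnancy (sibship) identifier, drawn from the birth history already being collected. It is easiest to capture prospectively.
- **Section 14:** add that, if any co-siblings are analysed, intervals and p-values will allow for clustering by mother, for example by a bootstrap that resamples mothers. At the least, add a sensitivity analysis that keeps one randomly chosen infant per pregnancy.
- **Reporting:** state the number of sibships with more than one analysed infant in each group.

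The cost is one CRF field, a little extra analysis work (possibly outside the basic SPSS procedures) and slightly wider intervals where co-siblings are present. Eligibility, measurements and care do not change. If no co-siblings enrol, the results are essentially unaffected.
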